8.2.1.3 Adverse Event Reporting Requirements

According to federal regulations, an Investigator must immediately report (within 24 hours) to the Sponsor any SAE, whether or not considered drug related, including those listed in the protocol or IB, and must include an assessment of whether there is a reasonable possibility that the drug caused the event. Study endpoints that are SAEs (e.g., all-cause mortality) must be reported in accordance with the protocol unless there is evidence suggesting a causal relationship between the drug and the event (e.g., death from anaphylaxis). In that case, the Investigator must immediately report the event to the Sponsor (See 21 Code of Federal Regulations [CFR] 312.64(b)).

According to federal regulations, the Sponsor must notify the US Food and Drug Administration (FDA) and all participating Investigators as soon as possible, but in no case later than 15 calendar days after the Sponsor determines that a potential serious risk arising from a clinical study qualifies for reporting. The Sponsor must report any suspected adverse reaction that is both serious and unexpected. The Sponsor must report an AE as a suspected adverse reaction only if there is evidence to suggest a causal relationship between the drug and the adverse event (See 21 CFR 312.32(c)(1)).

Furthermore, the Sponsor must also notify FDA of any unexpected fatal or life-threatening suspected adverse reaction as soon as possible but in no case later than 7 calendar days after the Sponsor's initial receipt of the information (See 21 CFR 312.32(c)(2)).

8.2.1.4 Other Events of Interest

Not applicable.

8.2.1.5 Pregnancy

All pregnancies are to be reported from the time informed consent is signed through Visit 6.

Any report of pregnancy for any female study subject must be reported within 24 hours to the Sponsor's Safety Department or its delegate using the Pregnancy Report Form. The pregnant female subject must be withdrawn from the study.

Every effort will be made to gather information regarding the pregnancy outcome and condition of the infant. It is the responsibility of the Investigator to obtain this information within 30 calendar days after the initial notification and approximately 30 calendar days after delivery.

Pregnancy complications such as spontaneous abortion/miscarriage or congenital abnormality are considered SAEs and must be reported to the Sponsor's Safety Department using the Serious Adverse Event Form. Note: An elective abortion is not considered an SAE.

In addition to the above, if the Investigator determines that the pregnancy meets serious criteria, it must be reported as an SAE to the Sponsor's Safety Department.

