3.1 Overall Design of the Study

This is a phase 2, multi-center, double-masked, randomized, vehicle-controlled, dose-response, parallel-group study designed to evaluate the ocular and systemic safety and ocular efficacy of SY-201 Ophthalmic Solution over a 60-day treatment period in subjects with moderate to severe DED.

During the 14-day single-masked run-in period, approximately 200 subjects will instill vehicle as 1 drop BID in both eyes (OU). At Visit 2, subjects will be randomized in a 1:1:1:1 ratio to 4 treatment groups: Vehicle (n=50) and SY-201 Ophthalmic Solution 2.0% (n=50), 1.0% (n=50), and 0.5% (n=50). Double-masked IP will be instilled as 1 drop OU BID for 60 days.

The study will consist of 6 clinic visits: Visit 1 (-14 Days, Screening), Visit 2 (Day 1, Randomization), Visit 3 (Day 7 ± 2 days), Visit 4 (Day 14 ± 2 days), Visit 5 (Day 28 ± 2 days), and Visit 6 (Day 60 ± 3 days, End of Study/Early Termination). A study schematic follows ([Figure 1](#)).

Figure 1: Study Schematic

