3.2 Rationale for the Study Design

This study will examine the ocular and systemic safety and ocular efficacy of SY-201 Ophthalmic Solution versus vehicle dosed OU BID for 60 days in subjects with moderate to severe DED.

SY-201 Ophthalmic Solution and vehicle will each be administered as a topical ophthalmic solution. In the single-masked run-in period, vehicle will be dosed OU BID by all subjects to normalize baseline conditions between subjects. Subjects will self-administer the first dose in-clinic at Visit 1 and all remaining doses at home. In the double-masked treatment period, subjects will self-administer 1 dose of IP in-clinic at Visit 2 (Day 1) and Visit 6 (Day 60) and all remaining doses at home, OU BID.

Direct instillation is the most efficient method for delivery to the ocular surface and is an accepted and widely used method for topical application to the eye. Each dose will be delivered by administering 1 drop (in each eye from a single-use vial.

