4.1 Inclusion Criteria

Individuals will be eligible for study participation if they meet all of the following criteria:

1. Provide written informed consent prior to any study-related procedures.
2. Are 18 years of age or older.
3. Are willing and able to follow instructions and can be present for the required study visits for the duration of the study.
4. Have a BCVA in each eye, using corrective lenses if necessary, of +0.7 logarithm of the minimum angle of resolution (LogMAR) or better as assessed by the Early Treatment of Diabetic Retinopathy Study (ETDRS) at Visit 1.
5. If women of childbearing potential (WOCBP), are non-lactating and have been sexually inactive (abstinent) for 14 days prior to Visit 1 and remain so through 30 days following Visit 6 or the last administration of the study drug or until completion of the subject's first menstrual cycle following the last administration of the study drug, whichever period of time is longer. Or they must have been using one of the following acceptable methods of birth control for the times specified:
 - a. Intra-uterine device (IUD) in place for at least 3 months prior to Visit 1 through 30 days following Visit 6 or last administration of study drug or until completion of the subject's first menstrual cycle following last administration of the study drug, whichever period of time is longer.
 - b. Barrier method (condom or diaphragm) with spermicide for at least 14 days prior to Visit 1 through 30 days following Visit 6 or last administration of the study drug or until completion of the subject's first menstrual cycle following last administration of the study drug, whichever period of time is longer.
 - c. Stable hormonal contraceptive for at least 3 months prior to Visit 1 through 30 days following Visit 6 or last administration of the study drug or until completion of the subject's first menstrual cycle following administration of the study drug, whichever period of time is longer. Note: For Depo-Provera injection contraceptives, the statement regarding first menstrual cycle following

administration of the study drug is not applicable, as females receiving this form of contraception will not have menses.

- d. Surgical sterilization (vasectomy) of partner at least 6 months prior to Visit 1.
- 6. If postmenopausal women, have had no menstrual cycle for at least 1 year prior to Visit 1 or have undergone one of the following sterilization procedures at least 6 months prior to Visit 1:

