7.1 Visit Descriptions

7.1.1 Screening (Visit 1, -14 days)

Ocular assessments and procedures must be performed in the order specified below. Tasks marked with an asterisk may be performed at any point (at Visit 1, after the consent is signed).

- Explain the purpose and conduct of the study to the subject, answer the subject's questions, and obtain written informed consent and HIPAA authorization.
- Assign Subject Identification Number.
- Obtain information including: demographics, CMs, ocular and systemic medical and medication history and surgical history.
- Determine study eligibility based on Inclusion/Exclusion criteria.
- Administer the following subject-rated symptom assessments:
 - Urine pregnancy test (UPT) for WOCBP*
 - Safety labs: blood samples for chemistry and hematology*
 - BCVA
- Biomicroscopy and external eye exam
- OU tear collection under slit lamp for biomarker test (quantitative point-of-care [POC] MMP-9 test by Seinda Biomedical Corp.)
- CFS
 - **Note:** After CFS grading, wait at least 15 minutes before conducting
- IOP
- Dilated ophthalmoscopy
- Enter subject information into EDC to determine the single-masked run-in kit number.
- Dispense 3 kits of single-masked run-in product (sufficient for up to 15 days) and explain the method of run-in administration.

- Observe as the subject self-administers the first dose (1 drop OU) of single-masked run-in at the clinic. All remaining doses (1 drop OU BID) will be administered by the subject at home.
- Assess for AEs.
- Remind subject:
 - Use of AT during the run-in period is prohibited. Use will result in subject's discontinuation from the study.
 - Run-in product should be administered as 1 drop OU once in the morning and once in the evening, 8-12 hours apart. **Do not dose run-in product the day of Visit 2.**
 - Return all used and unused run-in product at Visit 2.

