8.2.1 Adverse Events (AEs) and Serious Adverse Events (SAEs)

Adverse events will be monitored throughout the study. Subjects will be encouraged to report any adverse findings during the study whether or not they are related to IP. These can be collected either in an unsolicited fashion without any prompting or in response to a general question such as: "Have you noticed anything different since you started the study; began the IP, etc.?"

All AEs will be captured on the appropriate case report form (CRF). Information to be collected at minimum includes event description, onset, assessment of severity, relationship to IP, and outcome.

The Investigator will record all AEs with start dates occurring any time after informed consent is obtained until 7 (for nonserious AEs) or 30 days (for SAEs) after the last day of study participation. At each study visit, the Investigator will inquire about the occurrence of AE/SAEs since the last visit. Events will be followed for outcome information until resolution or stabilization.

Any medical condition that is present at the time that the subject is screened will be considered baseline and not reported as an AE. However, if the subject's condition deteriorates at any time during the study, it will be recorded as an AE.

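### Mandatory pregnancy reporting ends at Visit 6, at least 30 days before the contraception, SAE and TEAE windows close for completers, so an uncomplicated pregnancy first recognised later carries no clear duty to report

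*Protocol*

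**What the plan says.** Protocol 8.2.1.5 defines the reporting window: "All pregnancies are to be reported from the time informed consent is signed through Visit 6". The next paragraph of that section requires a pregnancy report to reach the sponsor's safety department within 24 hours and gives no end date of its own. The section also asks for outcome information, timed from the first notification and from delivery. It classes miscarriage and congenital abnormality as SAEs.

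Other windows run longer:

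- **Contraception (Protocol 4.1, item 5).** Women of childbearing potential who rely on abstinence must "remain so through 30 days following Visit 6 or the last administration of the study drug", or until their next menstrual cycle has finished, "whichever period of time is longer". The IUD, barrier and hormonal options carry the same end point, with a note that the menstrual part does not apply to one injectable contraceptive. The remaining option, "Surgical sterilization (vasectomy) of partner at least 6 months prior to Visit 1", states no post-dose period.
- **AE and SAE recording (Protocol 8.2.1).** Events are recorded "until 7 (for nonserious AEs) or 30 days (for SAEs) after the last day of study participation".
- **TEAEs (SAP 9.7.1.6.1).** The window closes 30 days after the last double-masked dose.

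On timing, Protocol 3.1 gives "Visit 6 (Day 60 ± 3 days, End of Study/Early Termination", and Protocol 3.2 says "subjects will self-administer 1 dose of IP in-clinic at Visit 2 (Day 1) and Visit 6 (Day 60". Pregnancy testing, listed at screening as "Urine pregnancy test (UPT) for WOCBP", is scheduled at Visits 1 and 6 only (Protocol 7.1.1, 7.1.6 and Appendix 1). SAP 9.7.1.6.2 lists the test results.

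**The concern.** For a completer, the duty to report a pregnancy closes on the day dosing ends. The protocol still requires contraception for at least 30 more days, and the other serious-event windows stay open for 30. A woman who conceives near the end of dosing may not know it at Visit 6. If she learns of it a week later and the pregnancy is uncomplicated, no sentence clearly obliges the site to report it.

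The outcome follow-up in 8.2.1.5 depends on a notification, so a pregnancy that is never notified triggers no enquiry about delivery or the infant. What is at stake is safety information on exposed pregnancies, which cannot be recovered later. Sample size, power, type I error and the efficacy estimates are not involved.

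**Working it through.** The plan gives no figure to reproduce. The check sets the windows side by side.

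**1. End dates for a completer.** Visit 6 falls between Day 60 − 3 = 57 and Day 60 + 3 = 63, and the last dose is given that day.

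| Window | Source | Rule | Closes |
|---|---|---|---|
| Pregnancy reporting | Protocol 8.2.1.5 | Visit 6 | Day 57 to 63 |
| Nonserious AEs | Protocol 8.2.1 | last day of participation + 7 | Day 64 to 70 |
| SAEs | Protocol 8.2.1 | last day of participation + 30 | Day 87 to 93 |
| TEAEs | SAP 9.7.1.6.1 | last dose + 30 | Day 87 to 93 |
| Contraception (except partner vasectomy) | Protocol 4.1, item 5 | Visit 6 or last dose + 30, or next cycle if longer | Day 87 to 93 or later |

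The gap is 87 − 57 = 93 − 63 = 30 days against the SAE and TEAE windows, and 30 days or more against contraception. Even nonserious AEs are recorded for 7 days longer than pregnancies.

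**2. What is still caught.**

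- A pregnancy detectable by the Visit 6 urine test, because Visit 6 lies inside the reporting window.
- A miscarriage or other complication starting within 30 days of the end of participation. It is an SAE under 8.2.1.5 and recorded under 8.2.1, and neither section makes this depend on an earlier pregnancy report.
- Possibly a pregnancy that a site chooses to report later, through the undated 24-hour sentence.

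**3. What is left.** Uncomplicated pregnancies first recognised after Visit 6, from two sources:

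- (a) conceptions late in dosing, too recent to test positive at Visit 6;
- (b) conceptions after the last dose, within the contraception period.

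**4. Size of (a).** Let d be the number of days before Visit 6 in which a conception would still test negative. The documents do not give d; I assume 7 to 14. The share of the 60-day treatment period is d/60:

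- d = 7: 7/60 = 11.7%, about 12%
- d = 14: 14/60 = 23.3%, about 23%

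This is a share of treatment days. It equals a share of on-treatment conceptions only if these are spread evenly over the 60 days. The number of women of childbearing potential is not stated, so an expected count cannot be derived.

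**5. How far the SAE route reaches.** A conception on Day 1 is at most 93 − 1 = 92 days old when the SAE window closes, and the pregnancies in step 3 are younger. The route can therefore catch an early loss. It cannot stand in for follow-up to delivery, where a congenital abnormality would ordinarily be found.

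**6. Early stoppers.** Protocol 6.1 and 7.1.8 bring the Visit 6 assessments forward when a subject leaves early, so pregnancy reporting closes correspondingly early.

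**The case against.** The strongest reply is that the residual gap is small. Women of childbearing potential are tested at Visit 6, they must use contraception or abstain, a quarter of subjects receive vehicle, and complications in the following 30 days are SAEs in any case. The 24-hour sentence has no end date and can be read as covering a later report. Once a pregnancy is notified, follow-up runs to about 30 days after delivery. All of this stands, and it limits the point to uncomplicated pregnancies first recognised after Visit 6. It does not close the gap. The undated sentence follows directly on one that sets an end date, so the section is ambiguous at best.

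A reader might infer more than the documents support:

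- **That all pregnancies exposed late in treatment go uncaptured.** The Visit 6 test contradicts this.
- **That the loss is larger.** Assuming recognition takes 2 to 4 weeks gives 14/60 = 23% to 28/60 = 47% of treatment days, but that ignores active testing at the cut-off.
- **That complications go unreported because the pregnancy was never reported.** The SAE duty has no such condition.
- **That the 30 days reflect a documented reproductive risk.** Protocol 4.1 gives no reason for the period, and no text is visible under Protocol 1.3.1, so the size of any such risk cannot be judged here.

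**Conclusion.** The windows do not agree, and no visible text explains why pregnancy should have the shortest. Read literally, 8.2.1.5 leaves uncomplicated pregnancies first recognised after Visit 6 without a clear duty to report. The undated 24-hour sentence makes the section ambiguous rather than silent, so capture after Visit 6 would be incidental.

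The mismatch is 30 days for completers, or more where the next menstrual cycle sets the contraception end date. The 12% to 23% figure covers only late-dosing conceptions and rests wholly on the assumed 7 to 14 days of test insensitivity; conceptions after the last dose come on top of it. Few events are expected among about 200 adults. This is a safety-reporting inconsistency worth correcting, and it has no bearing on the efficacy conclusions.

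**What to change.** Reconcile Protocol 8.2.1.5 with Protocol 4.1, Protocol 8.2.1 and SAP 9.7.1.6.1:

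- Extend the reporting duty past Visit 6 to a window the protocol already uses: at least the 30-day SAE window, or the contraception window. Name the one chosen, because they differ. SAE recording stops at a fixed 30 days, while contraception can run longer with the menstrual cycle. Nothing scheduled after Visit 6 would record that later end date.
- State that 24-hour reporting and outcome follow-up apply to pregnancies reported in the extended window.
- Say how the window applies to subjects who leave early.
- Add a matching line to the consent form and site instructions, so that subjects know to call and sites know to report.

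The cost is a sentence or two of protocol text, the matching instructions and a slightly longer period of passive reporting. No visit or test is added. Because capture stays passive, a pregnancy that nobody reports will still be unknown.

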8.2.2 Clinical Laboratory Tests

The following clinical laboratory tests will be performed at the time points indicated on the Schedule of Procedures and Assessments ([Appendix 1](#)) and as detailed below and in the laboratory reference manual.

- Chemistry

- Sodium, Potassium, BUN, Creatinine, Glucose, Calcium, Phosphorus, Total Protein, Albumin, AST (SGOT), ALT (SGPT), Alkaline Phosphatase, Total Bilirubin, Chloride, Bicarbonate
- Hematology
 - Hemoglobin, Hematocrit, RBC, MCH, MCHC, RDW, WBC, Neutrophils, Lymphocytes, Monocytes, Eosinophils, Basophils, Platelets

9. Statistical Considerations

Continuous measures will be summarized descriptively by the mean, standard deviation, median, minimum, and maximum values. Categorical measures will be summarized by the frequency and percentage of subjects.

A separate Statistical Analysis Plan (SAP) will be prepared prior to unmasking of study data.

9.1 Statistical Hypothesis

It is hypothesized that SY-201 Ophthalmic Solution will be safe and improve DED signs and symptoms in subjects with a documented diagnosis of DED. In particular, efficacy will be assessed using the following endpoints at Day 60:

- Mean CFB in tCFS (mNEI scale)

To control for type I error, comparisons will be made within each active dose level of SY-201 Ophthalmic Solution compared to vehicle. In other words, the primary endpoints will be compared sequentially between SY-201 Ophthalmic Solution 2.0% and vehicle, first testing tCFS and, if statistically significant, then [REDACTED] Should both endpoints achieve statistical significance for the 2.0% dose, testing will proceed to SY-201 Ophthalmic Solution 1.0% versus vehicle, first testing tCFS and, if statistically significant, then [REDACTED]. Should both endpoints achieve statistical significance for the 1.0% dose, testing will proceed to SY-201 Ophthalmic Solution 0.5% and vehicle, first testing tCFS and, if statistically significant, then [REDACTED]. In other words, the first non-significant result in this testing hierarchy of six hypotheses will imply that subsequent tests are non-significant.

9.2 Sample Size Determination

For mean change from baseline to Day 60 in tCFS, a sample size of 45 SY-201-treated subjects versus 45 vehicle-treated subjects will have 87.9% power to detect an effect size of 2.0 units with a standard deviation of 3.0 for an unpaired t-test with a 2-sided alpha = 0.05.

For mean change from baseline to Day 60 in dry eye symptom [REDACTED], a sample size of 45 SY-201-treated subjects versus 45 vehicle-treated subjects will have 83.5% power to detect an effect size of 1.5 units with a standard deviation of 2.4 for an unpaired t-test with a 2-sided alpha = 0.05.

Fifty (50) subjects per treatment arm, for a total 200 subjects, will be enrolled to allow for some dropout of subjects.

9.3 Analysis Populations

The Full Analysis Set (FAS) consists of all subjects analyzed in the group to which Subjects will be
This set will be used for the analysis of all efficacy endpoints as the primary analysis.

The Per Protocol (PP) Analysis Set will include all subjects who completed study-required treatment and who followed the protocol without significant deviations. The determination of significant protocol violations will be made prior to locking the final database and unmasking. Subjects will be analyzed in the group according to the treatment received.

The Safety Analysis Set will include all subjects who took at least one dose of investigational product as indicated on the dosing record. Subjects will be analyzed in the group according to the treatment received. All safety variables will be analyzed using the Safety Analysis Set and only observed data will be included (i.e., missing data will remain missing for the safety analysis).

9.4 Statistical Analyses

The statistical analysis of the study will be performed on the data through Day 60, after all subjects have either completed the Day 60 visit or discontinued early from the study and after the study database has been cleaned, verified, and locked. It is planned that the data from all clinical sites that participate in this study will be combined so that the target sample size will be available for analysis.

Analyses will be conducted on individual SY-201 arms versus vehicle arm.

9.4.1 Baseline Descriptive Analyses

Demographic characteristics including age (years), sex, race, and ethnicity will be summarized by treatment group and overall. Medical history [coded using the most recent version of the Medical Dictionary for Regulatory Activities (MedDRA)], and prior and concomitant medications (coded using the most recent version of the WHO Drug) will be summarized by treatment and overall.

The numbers of subjects who were enrolled and completed each visit of the study will be provided, as well as the reasons for all enrollment discontinuations, grouped by major reason (e.g., lost to follow-up, adverse event, poor compliance, rescue due to lack of efficacy). A list of discontinued subjects, protocol deviations, and subjects excluded from the analysis sets will be provided as well.

Exposure and compliance to study treatment will be summarized by treatment and overall.

